### **METHODS**

**Setting:** The study will be conducted in two cities, New York and Indianapolis, in the EDs of their respective academic institutions—NYU Langone Medical Center and Indiana University Health University Hospital. The NYU Ronald O. Perleman Center for Emergency Services sees >60,000 patients annually. In 2015 the numbers of ED patients >75 years who were discharged to home were >3700 in the NYU ED and 2400 patients in the Indiana University Eskanazi and Methodist EDs.

**Aim1: Recruit and randomize a sample of 900 patient-caregivers (CGs) dyads (1800people total) presenting to the ED and test whether the POISED intervention will reduce recurrent acute care use over 6 months when compared with post-ED care for patients and CGs without POISED.**

**Study Design:** We will randomize subjects to either usual care or interventional groups where we will perform an initial assessment and provide a novel care management intervention for family CGs of ED users with cognitive impairment and likely ADRD.

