Specific Aim 2: We will use mixed effects models with CG activation scores at 3 months and 6 months as the outcome measure and randomization group as the independent variable while controlling for baseline activation score and stratification variables (site, language, living arrangement and CRs' cognitive status). We will conduct post-hoc comparisons of the activation scores between the POISED group and the usual care group at 3 and 6 months using linear contrast from the mixed effects model following a significant group effect. To explore what changes are responsive to the POISED intervention, we will also use the mixed effects model to examine differences in activation domain scores between the two groups. The mixed effects

model will account for potential correlations between repeated measures from the same individual and deal with missing data appropriately when the probability of missing data is unrelated to the missing observation.

Specific Aim 3: We will use mixed effects models with repeatedly measured PHQ-9, GAD-7 and MOS social support scores collected at 3 and 6 months as dependent variables. The independent variable for the mixed effects model will be the indicator variable for the randomization group while controlling for baseline scores and stratification variables. We will use post-hoc analysis to determine group differences in these measures between the two groups at the 3- or 6-month evaluations. The modeling approach resembles that for Aim 2.

Sensitivity analysis for missing data: The analysis plan outlined above assumes that outcome measures at follow up are missing at random with respect to demographic characteristics and baseline results. We will compare baseline characteristics of subjects with missing outcomes due to death or withdrawal to detect potential violation of the missing-at-random assumption. Further sensitivity analyses will involve various imputation methods or a full parametric likelihood approach that assumes various patterns of missing data.

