Sample Size and Power Consideration: Sample size for the proposed study is estimated for achieving 80% power in reducing acute care use in the POISED group compared with the usual care group in Specific Aim 1. A previous study had reported a 30-day readmission rate of 58% in dementia patients as compared to 38% in those without dementia. Given that our patient sample may include less severe cognitive impairment with less ED use, we assume, conservatively, that the rate of ED visits in the usual care group is 40%. With 320 patients enrolled per group, we will have 82% power to detect an odds ratio of 0.62 for repeat ED visits in the POISED group compared to the usual care group at the 0.05 significance level. This detectable odds ratio is equivalent to reducing the ED visit rate to 29% or lower in the POISED group compared with the 40% assumed for the control group. The use of stratified randomization ensures that patients in the intervention and control groups are similar on the stratification variables, thus reducing the variance of the difference between the two group means and resulting in greater power than simple randomization. Therefore, actual power for our study will be higher than projected here. Since we will be using EMR for acute care data and phone follow-up to supplement out of network use, we anticipate complete data from all study participants for this aim.

For Aims 2 and 3, assuming that 205 (64%) dyads will complete the 6-month evaluation (see Figure 2), we will have 80% power to detect an effect size of 0.28 or greater on the CG activation score, PHS-9, GAD-7 and MOS scores between POISED group and the control group using a two-sample t-test at the 0.05 significance level. The detectable effect size of 0.28 used in our power estimation is reasonable and justified given that previous studies on collaborative care management of dementia patients have shown an effect size of 0.45 SD on a number of caregiver psychosocial outcomes. Our previous studies have found a mean PHQ-9 score of 4.4 (SD=5.6), and a mean GAD-7 score of 3.2 (SD=3.5). Thus our projected effect size will allow us to detect a change as small as 1.6 on the PHQ-9 and 1 on the GAD-7. As described above, the use of stratified randomization will provide greater power than those projected here.

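### For Aims 2 and 3, the planned baseline comparison cannot detect missingness that depends on the unseen score, the models omit covariates that the stated missing-at-random assumption names, and the promised sensitivity analysis is unspecified

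*Combined protocol and SAP*

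**What the plan says.** Under the sensitivity-analysis paragraph of the Statistical Plan, follow-up outcomes are assumed to be "missing at random with respect to demographic characteristics and baseline results". The stated check is: "We will compare baseline characteristics of subjects with missing outcomes due to death or withdrawal to detect potential violation of the missing-at-random assumption". The next sentence promises further analyses, either by unspecified imputation methods or by a likelihood model under differing patterns of missingness. Its citation is number 86, while the main reference list ends at 35.

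The Aim 3 mixed models are fitted "while controlling for baseline scores and stratification variables". Aim 2 is parallel: baseline activation score, site, language, living arrangement and care-recipient cognitive status. Adjustment for baseline characteristics that prove unbalanced between arms is written under Aim 1 only. The Specific Aim 3 Measures section says that the HABC-Monitor will be used to adjust for dementia symptom severity, but no model in the Statistical Plan includes it.

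The power section sizes Aims 2 and 3 "assuming that 205 (64%) dyads will complete the 6-month evaluation".

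**The concern.** Missing at random fails when, given what the model contains, missingness still depends on the score that was not observed. Observed baseline data carry no direct information on that. A difference between completers and non-completers refutes only missing completely at random. The absence of a difference leaves missing at random untested.

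A second gap lies between assumption and model. If missingness is taken to be ignorable given demographics, the analysis has to condition on them. Language and living arrangement are in the models. Age, gender, race and education, which the plan lists as baseline characteristics, are not.

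The caregiver results of Aims 2 and 3 are at stake, with over a third of 6-month scores expected to be missing. The Aim 1 outcome, which sizes the trial, is not affected: the plan expects complete data there.

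**Working it through.** **Inputs.** From the Statistical Plan: "With 320 patients enrolled per group"; 205 completers (64%); "we will have 80% power to detect an effect size of 0.28 or greater on the CG activation score", "using a two-sample t-test at the 0.05 significance level"; PHQ-9 SD 5.6. A two-sided test is assumed.

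**The plan's own figure.** 205/320 = 64.06%, so 205 is a per-group count and the loss is 1 − 0.6406 = 35.9%. SE = √(2/205) = 0.0988 SD. Power = Φ(0.28/0.0988 − 1.96) = 80.9% (80.7% with the exact t-test), which matches the stated 80%. Reading 205 as the total of both groups would give 51.8%.

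**Sensitivity to missingness.** Suppose the estimate under missing at random is 0.28 SD and the missing caregivers in POISED and usual care are worse than predicted by δP and δU. With equal loss in both arms, the adjusted effect is 0.28 − 0.359 × (δP − δU). Keep the completer SE, so the critical difference is 1.96 × 0.0988 = 0.194 SD, and set δU = 0:

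- Significance is lost at δP = (0.28 − 0.194)/0.359 = 0.24 SD, about 1.3 PHQ-9 points.
- The effect is zero at δP = 0.28/0.359 = 0.78 SD, about 4.4 PHQ-9 points.
- At an observed 0.45 SD, the figure the plan cites from earlier studies, significance is lost at (0.45 − 0.194)/0.359 = 0.71 SD.
- If δU = δP, the shifts cancel.

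The Methods section gives a different size: "Recruit and randomize a sample of 900 patient-caregivers (CGs) dyads". At 450 per arm and 64% retention, 288 complete, SE = √(2/288) = 0.0833, and significance is lost at (0.28 − 0.163)/0.359 = 0.32 SD. The 0.78 SD figure does not change.

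**What the baseline comparison can see.** This simulation rests on assumed parameters, not document figures: 320 per arm, 2,000 replicates, about 36% missing, no true effect, baseline–outcome correlation 0.5, demographic coefficient 0.3. The check is two t-tests at 0.05 (baseline score and one demographic), pooled over arms. The estimate is a regression at one follow-up on arm and baseline score, with or without the demographic. Bias is in SD.

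| Missingness depends on | Check flags | Bias, demographic omitted | Bias, demographic included |
|---|---|---|---|
| nothing | 10.6% | 0.00 | 0.00 |
| baseline score, alike in both arms | 100% | 0.00 | 0.00 |
| demographic, alike in both arms | 100% | 0.00 | 0.00 |
| demographic, opposite by arm | 9.3% | −0.10 | 0.00 |
| unseen part of outcome, alike in both arms | 10.0% | 0.00 | 0.00 |
| unseen part of outcome, POISED only | 9.1% | −0.19 | −0.19 |
| unseen part of outcome, opposite by arm | 9.2% | −0.37 | −0.37 |

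Two independent tests flag 1 − 0.95² = 9.8% by chance alone. The check therefore stays at its false-positive rate in every scenario with bias, and flags every replicate in two scenarios without bias. Run pooled, it also misses a demographic that acts in opposite directions by arm, which is the case where omission matters.

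**The case against.** **The plan goes beyond the check.** A reader might infer that the Aim 2 and 3 conclusions rest on the baseline comparison alone. They do not: analyses under differing missingness patterns are promised, and no rule says that a clean comparison settles the matter. This stands. What remains is that the promise gives no model, arm-specific assumption, shift range or reading rule, so the choice could be made after results are seen.

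**The check is not useless.** Relative to what the models contain, a baseline comparison can expose omitted predictors of dropout. This also stands. It is blind only to dependence on the unseen score.

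**Predicting dropout is not enough for bias.** A reader might infer that the models are invalid whenever age or education predicts dropout. The group contrast is biased only if the variable also predicts the outcome and acts on dropout differently by arm. The documents do not say that this is expected. It is plausible, since POISED brings home visits and regular calls while usual care receives referrals at enrollment, but it is not established.

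**The size is one scenario.** The calculation shifts POISED alone and uses a 6-month completer t-test. The planned mixed model also uses 3-month scores and baseline adjustment, and tests time-specific contrasts only after a significant group effect. The reasons for the expected loss are not given in the text; the power section refers to a Figure 2. All of this stands, so the figures illustrate fragility and do not predict bias.

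**Conclusion.** The point holds as one of method and specification. The stated check cannot detect the violation that matters, the Aim 2 and 3 models do not match the assumption they rely on, and the HABC-Monitor adjustment is not carried into them. The check also names only death and withdrawal, so missed interviews and lost contact are not clearly covered.

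With 35.9% missing at 6 months, an observed 0.28 SD effect would lose significance at a POISED-only shift of about 0.24 SD (0.32 SD if 900 dyads are randomized) and vanish at about 0.78 SD. These figures assume equal loss in both arms, the completer SE and no shift in usual care. The documents do not support a claim that the results will be biased, or that the plan ignores missingness related to the outcome.

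**What to change.** 1. Describe the baseline comparison as a search for predictors of missingness from any cause, not as a test of missing at random. Report it within each arm as well as pooled.
2. Prespecify caregiver age, gender, race, education, relationship to the care recipient and baseline HABC-Monitor as covariates in the Aim 2 and 3 mixed models, or in a multiple-imputation model fitted by arm. The analysis then matches the stated assumption and the Aim 3 measures section. Do not select covariates from the observed dropout.
3. Name a delta-adjusted (pattern-mixture) tipping-point analysis at 6 months as the sensitivity analysis, with shifts of 0 to 0.8 SD in POISED and varied in usual care too. Report the shift at which the conclusion changes.

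All these covariates are in the baseline survey. The cost is SAP wording and modest programming, with no new data.

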*Randomization:* A web-based randomization scheme will be used to randomize participants to intervention or usual care groups in blocks of four or six stratified by: site (NYU or IU), English or Spanish speaking, whether the care partner lives with the CR, and Mini-Cog™ score less than or equal to 3 (or IQCODE of >3.4).

. We assume a positive IQ-CODE score (>3.4) with an inability to complete a Mini- Cog™ is equivalent to a Mini-Cog™ score of 0.

*Initial assessment phase:* The POISED care management team consisting of specially-trained nurses functioning as care managers (CMs) and para-professionals in the role of care manager assistants (CMAs) will conduct a biopsychosocial/environmental needs assessment by phone within 48 hours of emergency room discharge if not possible during the ED stay. These team members are clinical professionals delivering a clinical service. They are not research staff or delivering experimental procedures. This assessment includes a demographic and psychosocial interview focused on achieving problem identification. The program uses standardized assessment tools including "Managing Your Loved One's Health" (MYLOH™) for chronic disease management and BEHAVE 5+ to identify problem behaviors common in advancing dementia that have been associated with caregiver strain, challenges to caregiving at home and in long-term care. BEHAVE 5+ also identifies proven behaviors common in prescribing of psychotropic medications to people with dementia. (See Appendix 3) If the consented CG is not available, we will attempt to complete the CG questions at a later date either by phone or in person.

*Root Cause Analysis:* Starting with the ED visit and working backwards in time, the team will explore and identify problems or branch-point situations that progressed to the need for ED care. Using a logic tree as a cause and effect approach to create a timeline of events leading to ED visit and asking the question, "how could this occur?" or "why" based on the "Five-Whys" strategy, the CM team will ask "why" for each successive answer, starting with "why did you come to the ED." Answers will be applied to medical record review looking for other possible triggers and opportunities for intervention. This brainstorming/investigative process to improve quality is also deployed by patient safety teams investigating adverse events.

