**Now I will ask you a few questions about traveling.**

9. We have [insert name of Care Recipient] address as [Fill In]. Is this correct?
10. What is the primary mode of transportation you use?

 Personal car	 Taxi
 Train	 Bus
 Walk	 Other ( please specify: _____)
11. Where do you go when you have to bring [insert name of Care Recipient] to see the doctor, meaning the doctor's office or clinic (usual source of care – USC) ? Do you have the location or address? \_\_\_\_\_
12. Where do you usually go if you need to travel to the hospital or Emergency Department (ED)? \_\_\_\_\_

*(For Calculating Miles and Difference in distance between ED vs. USC)*

**Next, I want you to think about the last 12 MONTHS and the care you have provided to [insert name of Care Recipient]. It might help to get a calendar.**

NOTE: FOR FOLLOW-UP SURVEYS, REPLACE "12 MONTHS" WITH THE CORRESPONDING TIME FRAME SUCH AS 3 MONTHS, 6 MONTHS

1. How many times did [insert name of Care Recipient], the person you care for, visit his/her Primary Care Provider or PCP in the last year? #\_\_\_\_ times
2. For each time, please indicate the primary reason for going to the PCP"

2a. Was the visit for a new symptom or for a change in a symptom that [insert name of Care Recipient]'s had previously?  Yes  No Acute use

2b. A fall or other injury?  Yes  No

2c. A symptom that has been present for more than the past month?  Yes  No Non-acute use

2d. A medication refill?  Yes  No

2e. Other (please specify: \_\_\_\_\_)

3. Have you had any difficulty getting medication refills for [insert name of Care Recipient]   
Yes  No
4. Over the past [insert time frame] has [care recipient name] had any new medical problems or illness?  Yes  No
5. Over the past [insert time frame] has [insert name of Care Recipient] had any injuries?   
Yes  No
6. How many times did he/she use the Emergency Department? #\_\_\_\_ times
7. How many times did he/she stay in the hospital overnight or longer in the last year? #\_\_\_\_ times

7a. For each stay in the hospital, I want you to tell me, to the best of your knowledge, the month and number of days he/she was in the hospital?

- i. Stay number 1: Month: \_\_\_\_\_. #\_\_\_\_ days
- ii. Stay number 2: Month: \_\_\_\_\_. #\_\_\_\_ days
- iii. Stay number 3: Month: \_\_\_\_\_. #\_\_\_\_ days

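### Aim 1 randomises 900 dyads, but every power figure in the sample-size section describes a trial of 640, and the text does not reconcile the two

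*Combined protocol and SAP*

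**What the plan says.** The Methods, under Aim 1, give the recruitment goal: "Recruit and randomize a sample of 900 patient-caregivers (CGs) dyads (1800people total"). The Randomization paragraph says the trial will "randomize participants to intervention or usual care groups in blocks of four or six" and gives no allocation ratio in words.

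The Statistical Plan, under Sample Size and Power Consideration, is the only place where a sample size is derived. For Aim 1 it assumes a 40% rate of ED visits under usual care and states: "With 320 patients enrolled per group, we will have 82% power to detect an odds ratio of 0.62 for repeat ED visits". It describes this odds ratio as "equivalent to reducing the ED visit rate to 29% or lower in the POISED group". It makes no allowance for loss on this outcome: "we anticipate complete data from all study participants for this aim".

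For Aims 2 and 3 the same section gives 80% power for an effect size of 0.28 by two-sample t-test at the 0.05 level, "assuming that 205 (64%) dyads will complete the 6-month evaluation". It does not say what the 64% is a percentage of, or whether 205 is per group or in total. It cites Figure 2 here, which is not shown in the text available.

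**The concern.** Both numbers are current text and both describe people entering the trial: one passage speaks of randomising 900 dyads, the other of 320 enrolled in each group. The wording therefore does not support reading 900 as randomised and 640 as evaluable. Nothing in the text takes 640 up to 900 or explains why 260 further dyads (520 people) are wanted.

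Two things follow. The power and detectable effects on record do not belong to the trial that Aim 1 describes. And stopping at 640 or at 900 could each be defended as following the plan, so a later reader could not check whether recruitment ended where intended.

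**Working it through.** **Inputs.** From the sample-size section: control rate p1 = 0.40, odds ratio 0.62, alpha 0.05, 320 per group, 205 completers, effect size d = 0.28. From Aim 1: 900 dyads. Assumed: a two-sided test (sidedness is not stated, but two-sided reproduces the plan's power) and 1:1 allocation, which the equal groups of 320 support. 900 dyads are then 450 per group.

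**Intervention rate.** Odds = 0.62 × 0.40/0.60 = 0.4133, so p2 = 0.4133/1.4133 = 0.2925. The plan's rounded 29% corresponds to (0.29/0.71)/(0.40/0.60) = 0.613.

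**Aim 1 power at 320 per group.** Two-proportion z test, pooled variance under the null:

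power = Φ{[(p1 − p2) − 1.96·√(2p̄(1 − p̄)/n)] / √([p1(1 − p1) + p2(1 − p2)]/n)}

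With p2 = 0.2925, p̄ = 0.3462 and n = 320, the two standard errors are 0.03761 and 0.03737. Then (0.1075 − 1.96 × 0.03761)/0.03737 = 0.905, and Φ(0.905) = 81.7%. The plan says 82%, so its figure is reproduced. An unadjusted logistic Wald test gives 81.3%.

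**The same formula at both sizes:**

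| Per group | Power at OR 0.62 | Power at 29% |
|---|---|---|
| 320 (640 dyads) | 81.7% | 83.5% |
| 450 (900 dyads) | 92.5% | 93.6% |

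The Wald test at 450 and OR 0.62 gives 92.2%. At 450 per group, 80% power is reached at p2 = 0.311, an odds ratio of 0.676. So 320 is the real basis of the stated 82% and not a misprint for 450.

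**Aims 2 and 3.** 205/320 = 64.1%, which matches the stated 64%; 205/450 = 45.6%, which does not. Two-sample t-test power at d = 0.28 is 80.7% with 205 per group (stated 80%), but 51.4% with 205 in total. The 205 must therefore be per group, on a base of 320. If 64% of 450 completed, that would be 288 per group, with 91.8% power at d = 0.28, or 80% power at d = 0.234.

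**Is there a step from 640 to 900?** It would need a loss of 1 − 640/900 = 28.9%, a rate found nowhere in the text. The one attrition figure, 36% for the 6-month interviews, gives 640/0.64 = 1,000, and it has already been applied to the 320.

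**Secondary check: tolerance to missing Aim 1 outcomes.** No loss rate is given, so this is only an assumed range, for an unadjusted comparison with loss unrelated to outcome. The n per group for 80% power is about 306 (OR 0.62) or 292 (29%). At 320 per group the tolerable loss is 1 − 306/320 = 4.4% to 1 − 292/320 = 8.8%. At 450 it is 1 − 306/450 = 32.0% to 1 − 292/450 = 35.1%.

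**The case against.** **Figure 2 may hold the derivation.** It is cited where enrolment becomes 205 completers, and its absence from the text available is not a fault of the plan. This stands as a limit on what can be said about a missing derivation. It does not remove the mismatch, because the text ties its power to 320 enrolled per group while Aim 1 randomises 900.

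**900 is the only stated recruitment goal, and 640 may be the minimum needed.** This is a possible reading. Against it, the sample-size section opens by saying that the study's size is estimated there, and it never mentions 900.

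**The surplus may cover dyads without usable records.** This is plausible. The care-recipient eligibility note and Recruitment, Consent and Assent let a caregiver take part without access to the care recipient's records, and refused records are described as missing data. The eligibility note also keeps data without proxy consent out of all analyses, and the Vulnerable Populations section lets a care recipient withdraw the caregiver's data later. But no passage offers this as the reason for 900, and the expectation of complete Aim 1 data runs against it.

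Nor is it settled whether the caregiver survey would fill such gaps. It asks "How many times did he/she use the Emergency Department", with the recall period replaced at follow-up "WITH THE CORRESPONDING TIME FRAME SUCH AS 3 MONTHS, 6 MONTHS". The Aim 1 measures and the sample-size section give telephone reports a supplementary role, for visits outside the regions or network searched. Data Collection and Documentation, and Appendix 1, treat the survey as a source in its own right. The main finding does not depend on this.

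**The practical effect is small.** This is fair. Power is adequate at either size with complete data, and the primary analysis is not affected.

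**Conclusion.** The inconsistency is real. The targets differ by 260 dyads (900 against 640), and all the power statements belong to 640. Each is correct at its own sample size. If 900 is meant, the stated power is conservative: 92.5% and not 82% for Aim 1 at an odds ratio of 0.62, and about 92% and not 80% for Aims 2 and 3 at d = 0.28 if 64% complete.

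This rests on a two-sided 0.05 test, 1:1 allocation, the plan's 40% control rate and complete Aim 1 data. The mismatch itself needs none of these assumptions. It should be fixed because a sample size and its power are wrong as written for one of the two stated targets, not because the trial is too small.

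**What to change.** State one randomisation target, with its derivation, in both Aim 1 and the sample-size section, and give the power that belongs to it.

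- **If 640 is meant:** change Aim 1 to 640 dyads (1,280 people) and keep the 82% power and the 0.28 effect size.
- **If 900 is meant:** state 450 per group, and 1:1 allocation if intended. Restate Aim 1 as about 92.5% power at an odds ratio of 0.62 (93.6% at 29%), or 80% power at about 0.68, with complete data. Restate Aims 2 and 3 as 288 completers per group at 64%, giving about 92% power at 0.28 or 80% power at about 0.23.
- **If 900 is 640 evaluable dyads inflated for loss:** state the assumed loss (about 29%) and its source, describe the 320 per group as evaluable and not enrolled, say what base the 64% applies to, and reconcile this with the expectation of complete Aim 1 data.

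In every case, name the base of the 64% and say that 205 is per group. The cost is a change of wording in one or two places. No further participants, visits or data are needed.
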